3.2 Statistical Analysis Issues

Every effort will be made by the Data Coordinating Center (DCC) to ensure complete, accurate, and high-quality data collection and annotation. However, as with all clinical trials, challenges are anticipated. Given the high mortality rate in this population, missing data is a key issue that may affect both primary and secondary endpoints (e.g., CMV reactivation [missing viral load values], organ dysfunction, and outcomes from the NHLBI-endorsed acute respiratory failure core measurement set). This section outlines the anticipated sources of missing data and corresponding mitigation strategies, informed by experience from the GRAIL Phase 2 trial.

Missing Data in Primary Outcome

Missingness in the primary outcome, RSFDs, is expected to be minimal (~2%) and is likely to be missing not at random (MNAR), primarily due to participant withdrawal of consent. Such withdrawals typically occur in more severely ill participants under high stress. Given the low expected frequency, missing data in RSFDs will be excluded from the primary analysis without imputation.

Missing Data in Some Secondary/Exploratory Outcomes Due to Study Design

Some secondary endpoints (e.g., static respiratory compliance) may be unavailable due to early extubation, ICU discharge, or death prior to scheduled biospecimen collection. For instance, if ganciclovir reduces respiratory support duration, extubated participants may not be eligible for endotracheal aspirates, potentially biasing the analysis. To minimize missingness, biospecimen collection was scheduled at Day 7 (± 1 day), when approximately 40% of participants are expected to remain alive and intubated. If missing data persist despite this timing, we will apply imputation techniques such as last observation carried forward (LOCF), multiple imputation (MI), or conduct sensitivity analyses. If missingness remains substantial, limitations will be acknowledged in interpreting results.

Missing Data in Covariates

Missing covariate data may result from death, withdrawal, or other causes. If covariate missingness exceeds 5%, it will be addressed analytically. Covariate missingness is expected to be MAR, and will be handled using either inverse probability weighting (IPW) or multiple imputation (MI) [1, 2].

- Weighting Adjustments:
 - Estimate the probability of missingness using logistic regression with baseline covariates as predictors.
 - Calculate IPW as the reciprocal of predicted probabilities.

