 - Apply weighted generalized estimating equations (WGEE) or weighted regression models to reduce bias in treatment effect estimates.
- Multiple Imputation (MI):
 - Use Multivariate Imputation by Chained Equations (MICE) to impute missing covariates.
 - Perform 20–50 imputations to ensure stability.
 - Combine estimates across imputations using Rubin's rules to derive valid statistical inference.

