5. GENERAL ANALYSIS METHODS

Primary Endpoint

To evaluate the primary hypothesis—that the mean difference in respiratory support-free days (RSFDs) between the two treatment groups is significantly different from zero—we will use a two-sample parametric t-test as the primary statistical test. This test is known for its robustness to violations of normality when the sample size is sufficiently large ($n > 25$), as is the case in this trial.

To support and validate the primary analysis, we will also conduct a two-sample permutation t-test. This nonparametric test requires only the assumption of exchangeability, which is satisfied in the context of a randomized controlled trial. The permutation test provides a distribution-free confirmatory approach, reinforcing the robustness of our findings.

In addition, we will apply the semiparametric efficient and robust estimation procedure proposed by Davidian et al. [7,8] to estimate the mean treatment difference in RSFDs along with a 95% confidence interval. This method adjusts for baseline covariates predictive of the outcome, thereby improving both statistical efficiency and precision relative to unadjusted comparisons or traditional ANCOVA. This analysis also accommodates missingness in the primary endpoint (excluding death) by explicitly modeling the missing data mechanism, as described in Protocol Section 6.4.1.

In addition to the primary analysis using the main intent-to-treat (ITT) population, we will conduct sensitivity analyses using the classical ITT (cITT) and two modified ITT (mITT) analysis sets to assess the robustness of results.

Secondary endpoints

For quantitative secondary endpoints, including the key secondary endpoint of ventilator-free days (VFDs), we will apply the same analytic approach as described for the primary endpoint (RSFDs), including both unadjusted and adjusted methods using the semiparametric efficient and robust procedure proposed by Davidian et al. [7, 8]. In addition, analyses will be conducted on total RSFDs without the last-off approach, to assess consistency across definitions.

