The absence of data pertaining to some secondary endpoints (for example, static respiratory system compliance) may be problematic if participants are discharged from the ICU, are on pressure support after being extubated, or expire prior to our pre-specified time points for endotracheal aspirates and serum collection. For example, if the Ganciclovir intervention reduces duration of respiratory support, it may bias the results because participants cannot undergo endotracheal aspirate if they are extubated. Thus, to minimize missing data and to maximize the CMV detection rate, we have selected multiple time points for the endotracheal aspirate (Day 1 and twice weekly until Day 28). If these issues still occur, we will address them in the analysis phase using data imputation methods, or by acknowledging it as a limitation of any analyses conducted with these variables.

6.4.1.3 Missing Data in covariates.

Missing data can occur in covariates as well, due to factors such as death, withdrawal, or other reasons; this will need to be accounted for in our analyses, if overall missingness (in covariates) increases beyond 5%. Since we expect covariate missingness in this study to be MAR (missing at random), we will use weighting adjustments (for example, weighted generalized estimating equations) or multiple imputation methods [98, 99] to deal with covariate missingness.

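### The SAP's inverse-probability weights for missing covariates are inverted: they are 1/P(missing) where 1/P(observed) is needed

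*SAP*

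**What the plan says.** SAP Section 3.2, under missing data in covariates, sets a trigger: "If covariate missingness exceeds 5%, it will be addressed analytically". Missingness is taken to be at random, and the analyst may use either inverse probability weighting or multiple imputation. The weighting option has three steps:

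1. "Estimate the probability of missingness using logistic regression with baseline covariates as predictors"
2. "Calculate IPW as the reciprocal of predicted probabilities"
3. "Apply weighted generalized estimating equations (WGEE) or weighted regression models to reduce bias in treatment effect estimates"

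The only probability defined before step 2 is the probability of missingness, so step 2 gives w = 1/P(missing). Neither document says that the complement is to be used. Protocol Section 6.4.1.3 covers the same ground in general terms ("we will use weighting adjustments (for example, weighted generalized estimating equations) or multiple imputation methods") and gives no weight formula, so it neither corrects nor contradicts the SAP.

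**The concern.** Inverse probability weighting lets each complete case stand in for similar patients whose data are missing. A patient with a high chance of being missing who was nonetheless observed must therefore count for more. The weight has to rise with P(missing), and 1/(1 − P(missing)) does. The SAP's weight falls as P(missing) rises. A complete case with a 3% chance of being missing gets weight 1/0.03 = 33, and one with a 17% chance gets 1/0.17 = 5.9.

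The affected analyses are those that use covariates:

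- the semiparametric covariate-adjusted estimate of the difference in respiratory-support-free days (RSFDs), the only RSFD analysis for which the SAP explicitly specifies a 95% confidence interval (SAP Sections 5 and 8);
- the multivariable models for RSFDs and secondary outcomes (SAP Section 5);
- the mortality Cox model adjusted for baseline creatinine clearance (SAP Sections 9 and 10).

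The Cox model shows how the trigger might be met. A footnote to protocol Appendix A waives serum creatinine for patients on renal replacement therapy, so this covariate may be missing mainly in those with the worst renal function. The written rule would then down-weight the observed patients most like them, in a mortality analysis of a trial whose enrolment was closed on safety and futility grounds (SAP Section 4). The documents do not give the proportion on renal replacement, so whether 5% would be exceeded is unknown.

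**Working it through.** The documents state no figure that depends on these weights, so there is nothing of theirs to reproduce. The check applies the three steps literally and compares the result with the standard weight. All missingness rates, stratum shares and effect splits below are assumptions. Only the 5% trigger and the 2.74-day difference (SAP Section 2.5) come from the documents.

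**Direction, in general.** Among all patients with P(missing) = p, a fraction 1 − p is observed. Their contribution to the weighted analysis is proportional to:

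- no weighting: 1 − p
- correct weight 1/(1 − p): (1 − p)/(1 − p) = 1, which restores the randomised mix
- SAP weight 1/p: (1 − p)/p

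The last falls in p more steeply than 1 − p does. Whenever p varies between patients, the written rule therefore tilts the sample in the same direction as no weighting, and further.

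**Two equal strata, 10% missing overall.** Sicker share = (1 − p_s)w_s / [(1 − p_s)w_s + (1 − p_m)w_m], where s is the sicker and m the milder stratum. Effective sample size (ESS) = (Σw)²/Σw².

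For 5% (milder) and 15% (sicker) missing, per patient randomised:

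- Unweighted share: 0.425/(0.475 + 0.425) = 47%
- SAP share: 0.475/0.05 = 9.50 and 0.425/0.15 = 2.83, so 2.83/12.33 = 23%
- SAP ESS: Σw = 12.33 and Σw² = 0.475/0.05² + 0.425/0.15² = 190.0 + 18.9 = 208.9, so 12.33²/208.9 = 73% of N

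| Missing, milder / sicker | Sicker share: unweighted | correct | as written | ESS: unweighted | as written |
|---|---|---|---|---|---|
| 5% / 15% | 47% | 50% | 23% | 90% | 73% |
| 3% / 17% | 46% | 50% | 13% | 90% | 63% |

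**Continuous severity score.** Let x be standard normal and logit p = −2.45 + 0.8x, which gives about 10% missing. Then (1 − p)/p = exp(2.45 − 0.8x), so the SAP-weighted score is normal with mean −0.80 SD. A simulation of 400,000 patients agreed: mean −0.08 SD unweighted, 0.00 with correct weights and −0.80 as written. ESS was 90%, 89% and 51% of N respectively.

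**Effect on the treatment difference.** This depends on whether the effect varies with severity. Two opposite assumptions, each averaging 2.74 days:

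- *Milder patients benefit more* (4.0 vs 1.48 days, equal strata). The estimate is 4.0 − 2.52 × sicker share. As written: 4.0 − 2.52 × 0.230 = 3.4 and 4.0 − 2.52 × 0.131 = 3.7. Unweighted: 2.8 in both cases. Correct: 2.74.
- *Sicker patients benefit more* (5.0 days in a sicker 30%, 1.77 in the rest):

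| Missing, sicker / other | As written | Unweighted | Correct |
|---|---|---|---|
| 10% / 4% (5.8% overall, just above the trigger) | 2.22 | 2.70 | 2.74 |
| 20% / 5% | 2.04 | 2.63 | 2.74 |
| 30% / 5% | 1.93 | 2.55 | 2.74 |

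In every scenario the written weights are further from the target than no weighting.

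**The case against.** The strongest reply is that this is loose wording. The SAP names a standard method under a stated missing-at-random assumption, and a logistic model for missingness also yields P(observed) as its complement. An analyst who looked at the weights would notice: at 5% missingness the written rule gives 20, whereas the correct weight is 1.05. That may describe the intent, but the SAP is the text to be programmed from, and following it produces inverted weights.

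The points about reach stand:

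- The rule operates only if covariate missingness exceeds 5% and weighting is chosen over multiple imputation, which is already specified.
- The SAP's primary test uses no covariates ("we will use a two-sample parametric t-test as the primary statistical test"), nor do the permutation test, the t-tests on secondary endpoints, the log-rank test or Gray's test.

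The size of any bias in the treatment effect is also not established. It needs an effect that varies with severity, which the documents do not give, and the two splits above push the estimate in opposite directions. If the effect is homogeneous and missingness depends on baseline covariates alike in both arms, the weights do not by themselves bias the randomised contrast; the cost is then mainly precision.

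**Conclusion.** The weighting rule is wrong as written. The direction of the error in sample composition is certain: wherever P(missing) varies, the weighted sample moves away from the patients it is meant to represent and ends up worse than an unweighted complete-case analysis. With 10% missing and the assumed patterns, the sicker half's share drops from a true 50% to 13–23%, and ESS to between 51% and 73% of N. Bias in the adjusted treatment difference is about 0.5 to 0.9 days either way under the assumed effect splits (1.93–2.22 or 3.4–3.7, against 2.74), and is not expected from this source if the effect is homogeneous. The primary test is untouched. The exposure is confined to covariate-adjusted analyses when the 5% trigger is met and weighting is used.

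**What to change.** Replace the first two weighting steps in SAP Section 3.2 with wording such as:

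> Estimate, by logistic regression on fully observed baseline variables, the probability that the covariates are observed. Weight each complete case by the reciprocal of that probability, 1/(1 − P(missing)), and use robust standard errors.

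Alternatively, delete the weighting option and rely on the multiple imputation already set out in the same section. Either change costs two lines of SAP text. Neither touches the primary test, the sample size or data collection. It should be made before any weighted analysis is programmed.

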2.1 General Design Considerations

The following is a summary of the protocol.

Short Title: A Phase 3 Study of Ganciclovir Use in Patients with Acute Respiratory Failure and Sepsis

Funder: NHLBI

Protocol Team: [name], PhD
 [name]
 [name]
 [name], MSc

Sample Size: Approximately 500 participants

Study Population: Immunocompetent, CMV seropositive adults hospitalized with sepsis and acute respiratory failure requiring respiratory support

Study Sites: Sites selected by the GRAIL Executive Committee

Study Hypotheses: We hypothesize that IV ganciclovir administered early in critical illness will effectively suppress CMV reactivation in CMV seropositive adults with sepsis-associated acute respiratory failure, thereby reducing lung damage and accelerating recovery from respiratory failure by direct and indirect mechanisms, and leading to improved clinical outcomes.

Study Design: Multicenter randomized placebo-controlled double-blind trial, [randomized in blocks for balance across study sites, with interim analyses of safety].

Study Duration: 180 days per patient

Study Product: Ganciclovir sodium: 2-amino-9-76,9-dihydro-3H-purin-6-one.
 Placebo for ganciclovir: [normal saline].

Study Regimen: 500 adults will be randomized in a 1:1 ratio to receive either the study drug or placebo. Participants randomized to intervention will use IV ganciclovir only. Participants will receive ganciclovir or normal saline twice daily from day 1 through day 5 and once a day from day 6 through day 28, hospital discharge, death, whichever occurs earlier.

		Schedule of administration*	
		Day 1 through Day 5	Day 6 through Day 28 or hospital discharge, whichever occurs earlier
Arm	N	Twice daily	Once daily
1	250	Ganciclovir 5 mg/kg intravenously	Ganciclovir 5 mg/kg intravenously
2	250	Normal saline intravenously	Normal saline intravenously
Total	500		

* "Day" on this table refers to study day. Day 1 is the first day of study drug administration.

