2.5 Sample Size and Power

To estimate the required sample size for this study, we used ventilator-free days (VFD) data from the GRAIL Phase 2 trial and available literature on RSFDs, assuming similar variance. A clinically meaningful difference in RSFDs between treatment arms was assumed to be 2.74 days, with an empirically estimated standard deviation of 9.4 days. To detect this difference with 85% power using a two-sided test at a 5% significance level, a total sample size of 426 participants (213 per group) was required for the primary analysis.

To account for feasibility and potential dropout—including 1% lost to follow-up and 2% early discontinuation due to negative CMV ELISA results—the final sample size was increased to 500 participants. A pre-specified sample size re-estimation was conducted after 50% of participants had reached the primary endpoint; based on the observed data, the original sample size was retained.

Mortality was included as a secondary endpoint. Assuming a 20% mortality rate in the control arm, the final sample size of 500 provides 80% power to detect a hazard ratio of 0.52 between the Ganciclovir and placebo groups.

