8. PRIMARY ENDPOINT ANALYSES

The primary endpoint, respiratory-support-free days (RSFDs), is defined as 28 days minus the number of days a participant received respiratory support (including invasive mechanical ventilation, non-invasive ventilation with CPAP or bi-level CPAP and PEEP ≥ 5 cmH₂O, or high-flow nasal cannula oxygen with a flow rate ≥ 30 L/min) through Day 28 following randomization.

- Participants who do not survive through Day 28 will be assigned zero RSFDs.
- Participants who remain on respiratory support on Day 27 will be assigned zero RSFDs.
- Participants transferred to long-term acute care hospitals (LTACHs) will be assigned zero RSFDs.
- Participants who withdrew consent, refused further participation by themselves or a legally authorized representative (LAR), and for whom no further data were collected, or who withdrew due to study closure within the first 28 days will be considered missing for the RSFD endpoint.

RSFDs will be summarized descriptively using the mean, standard deviation, median, and range by treatment group. To formally test the primary hypothesis that the mean difference in RSFDs between treatment arms differs from zero, a two-sample parametric t-test will be used. This test is appropriate even if the normality assumption is mildly violated, given its robustness for moderate sample sizes ($n > 25$). As a confirmatory approach, a two-sample permutation t-test will also be performed. This nonparametric test does not require distributional assumptions and is valid under the weaker condition of exchangeability, which is satisfied in the randomized trial setting.

To further improve statistical efficiency and precision, the semiparametric efficient and robust method of Davidian et al. [7, 8] will be employed to estimate the mean difference between arms, along with its 95% confidence interval. This method adjusts for baseline characteristics predictive of the primary outcome and is more powerful than a conventional ANCOVA or t-test when baseline adjustment is warranted. If data on

the primary endpoint are missing for reasons other than death, the analysis will appropriately account for the missing data mechanism, as described in Protocol Section 6.4.1.

In addition to the ITT analysis, the primary endpoint will also be analyzed in a classical intent-to-treat (cITT) and two modified intent-to-treat (mITT) populations.

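### SAP 3.2 leaves covariate missingness of 5% or less unaddressed and above that allows a misdirected, baseline-only weighting, which can shrink a mortality-driven difference in the supportive adjusted RSFD estimate

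*SAP*

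**What the plan says.** On causes, SAP section 3.2 (Missing Data in Covariates) states: "Missing covariate data may result from death, withdrawal, or other causes". On the trigger: "If covariate missingness exceeds 5%, it will be addressed analytically". Nothing is said about missingness at or below that level. Above it, the section assumes missing at random and allows weighting or multiple imputation without saying which applies when.

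- Weighting: the model is specified as "Estimate the probability of missingness using logistic regression with baseline covariates as predictors". The next bullet takes the reciprocal of the predicted probabilities, and the one after applies weighted GEE or weighted regression.
- Imputation: "Use Multivariate Imputation by Chained Equations (MICE) to impute missing covariates", with 20–50 imputations and Rubin's rules. The variables in the imputation model are not listed.

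Protocol section 6.4.1.3 also offers weighting or multiple imputation above 5%, but does not restrict the weight model to baseline covariates.

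Covariates enter the RSFD analysis through the semiparametric estimate in SAP sections 5 and 8, to which the SAP attaches the 95% confidence interval: "This method adjusts for baseline characteristics predictive of the primary outcome". They also enter the multivariable models in section 5. The primary test is an unadjusted two-sample t-test, confirmed by a permutation t-test. SAP section 8 assigns zero RSFDs to anyone who dies by day 28, so a death is an observed outcome.

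**The concern.** The stated cause and the stated remedy do not fit together. If a covariate is missing because the participant died, and baseline variables do not fully explain that, then missingness depends on the outcome. A weight model that contains only baseline covariates cannot restore the deaths it loses, even with correctly formed weights.

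The weights are also written the wrong way round. The model predicts missingness, and its reciprocal gives the largest weight to observed participants who were least likely to be missing. Representing the missing participants requires 1/P(observed) = 1/(1 − P(missing)).

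At or below 5%, no handling is stated. A model that needs the covariate would by default omit the participant, although the RSFD is known.

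What is at stake is the adjusted RSFD difference and its interval. If mortality differs between arms, more zeros are lost from the arm with more deaths, and that arm's mean rises by more.

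**Working it through.** **Plan's own figure.** SAP section 2.5 gives the effect and spread as "was assumed to be 2.74 days, with an empirically estimated standard deviation of 9.4 days" and continues "To detect this difference with 85% power using a two-sided test at a 5% significance level, a total sample size of 426 participants". The two-sample t calculation gives 212.3, rounded up to 213 per arm, so 426 reproduces. This concern does not affect it.

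**Inputs.** Control mortality is 20% (SAP section 2.5). Deaths score 0 (SAP section 8). The survivor mean m is an assumption: the phase 2 control VFD mean of 16.33 (protocol Table 6-1) divided by survival of 0.85 (15% phase 2 mortality, protocol Table 6-3) gives 19.2 days. Ganciclovir mortality and the share f of deaths with a missing covariate are assumptions; the documents give neither.

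**Closed form, missingness confined to deaths, same f in both arms.** With mortality p, the full mean is (1 − p)m and the complete-case mean is (1 − p)m / (1 − fp). Overall missingness is f times the average mortality.

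Example: mortality 20% against 30%, 10% missing overall, so f = 0.10/0.25 = 0.40.
- Full data: 13.44 − 15.36 = −1.92.
- Complete case: 13.44/0.88 − 15.36/0.92 = 15.27 − 16.70 = −1.42, an attenuation of 26%.

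| Ganciclovir mortality | Full data | 5% missing | 10% missing |
|---|---|---|---|
| 25% | −0.96 | −0.83 (14%) | −0.66 (31%) |
| 30% | −1.92 | −1.70 (11%) | −1.42 (26%) |
| 15% (benefit) | +0.96 | +0.76 (21%) | +0.51 (47%) |
| 20% (no effect) | 0 | 0 | 0 |

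The percentages do not depend on m, because it cancels. If mortality rises from 20% to 30% while survivors gain 2.74 days, a full-data difference of about 0 becomes +0.34 at 5% missing and +0.76 at 10%.

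**Does the weighting repair it?** Simulation of 400,000 patients, mortality 20% against 30%, 10% missing, linear-regression adjustment:

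| Analysis | Difference (days) |
|---|---|
| Unadjusted contrast (as in the t-test) | −1.85 |
| Adjusted, full data | −1.85 |
| Adjusted, complete case | −1.39 |
| Baseline-only weights, 1/P(observed) | −1.40 |
| Weights as the SAP writes them, 1/P(missing) | −1.34 |
| 1/P(observed), death in the weight model | −1.85 |
| Multiple imputation with arm, death and RSFD | −1.86 |

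**Second simulation.** 1,500 trials of 500 patients, mortality 20% against 28%, 2% of survivors also missing the covariate, full-data difference about −1.5:
- 15% of deaths missing (5% overall): complete case −1.44, about 4% too small.
- 30% of deaths (9% overall): complete case −1.27, correctly directed baseline-only weights −1.30, about 15% too small.
- 50% of deaths (13.5% overall): −1.05 and −1.10, about 30% too small.
- Simple imputation of the covariate: −1.51 to −1.52.

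A hand check of the last two missingness levels with m = 20 uses arm mean = (1 − p)(0.98)m / [(1 − p)(0.98) + p(1 − f)]. It gives −1.60 in full, −1.32 at f = 0.30 (18%) and −1.05 at f = 0.50 (34%), slightly more than simulated.

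**If missingness is unrelated to outcome.** Power for 2.74 days at SD 9.4 is 90% with 250 per arm and 88% with 230 per arm (8% dropped).

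**The case against.** The strongest reply is that the premise hardly applies to the covariates in question. Protocol section 9.6 places baseline bloods, APACHE III and SOFA before study drug. Section 9.5 requires date of birth, race/ethnicity and gender at randomization, with the first dose on the same calendar day. A later death cannot erase a value already recorded. A baseline endotracheal aspirate is absent because the patient is not intubated. The SAP's remark about death, and its mention of weighted GEE, may fit post-baseline covariates better.

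Much of this stands, and it limits the likely size. It does not settle the matter. Study-entry samples have a window of ±1 day (protocol section 9.9). Prior viral load is among the listed covariates (protocol section 5.3). Creatinine is not required during renal replacement therapy (Appendix A), although SAP section 9 adjusts the mortality model for baseline creatinine clearance. The documents do not establish a link between these gaps and death.

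It is also fair that multiple imputation is already an equal option and keeps every participant. The gap there is narrower: no rule for choosing it and no stated imputation model. The shifts are also modest against a standard error of about 9.4 × √(2/250) = 0.84 days: about 0.06 days at 5% missing and 0.23 days at 9% in the second simulation.

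Three stronger readings are tempting and not supported:
- That the primary result is biased. The t-test and permutation test use no covariate.
- That the SAP orders participants to be dropped. It is silent at or below 5%; exclusion is an inference.
- That a harm is understated, given that SAP section 4 records closure over safety and futility concerns. This needs higher ganciclovir mortality and death-related missingness beyond what baseline variables explain. The same mechanism shrinks a mortality benefit.

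**Conclusion.** The point holds for the supportive covariate-adjusted RSFD analysis only. The weighting option is misdirected as written. Even when corrected to 1/P(observed), it recovers almost nothing if death drives missingness (−1.40 against −1.85).

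The size rests on assumed missingness rates and assumed mortality differences. In the harm scenarios, attenuation is about 4–14% at 5% overall missingness and about 15–31% at 9–13.5%, with 34% from the hand check at the top end. In the one benefit scenario it is proportionally larger (21% at 5%, 47% at 10%). With equal mortality and no survivor effect there is no bias. The simulations used linear regression rather than the planned semiparametric estimator, so they show the mechanism and rough size, not a forecast. Where missingness has nothing to do with outcome, the loss is a little precision.

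**What to change.** Replace the 5% rule and the covariate weighting bullets in SAP section 3.2 with wording to this effect: *no participant with a known outcome is excluded from an adjusted analysis because a baseline covariate is missing; baseline covariates are imputed at any level of missingness, either by single imputation from other baseline variables (without arm or outcome) or by MICE with arm, RSFD and vital status in the imputation model.* Name one of the two as the method.

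If weighting is kept for any covariate, define the weight as 1/P(observed) and include arm and vital status or RSFD in the weight model.

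Report covariate missingness by arm and vital status, so that the reader can judge whether any of this matters in the data.

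The cost is SAP wording. The programming is slightly simpler than weighting, and the primary analysis and sample size do not change.
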